Appendix 6 Abnormal Laboratory Values

ABNORMAL LABORATORY VALUES RATING: SERUM CHEMISTRY
PARAMETERS

Serum Chemistry*	Mild (Grade 1)	Moderate (Grade 2)	Severe (Grade 3)
Sodium – Hyponatremia (mmol/L) ** ⁽¹⁾	<LLN - 130	-	<130 - 120
Sodium – Hypernatremia (mmol/L) ** ⁽¹⁾	>ULN - 150	>150 - 155	>155 - 160; hospitalization indicated
Potassium – Hyperkalemia (mmol/L)** ⁽¹⁾	>ULN - 5.5	>5.5 - 6.0	>6.0 -7.0; hospitalization indicated
Potassium – Hypokalemia (mmol/L) ** ⁽¹⁾	<LLN - 3.0	<LLN - 3.0; symptomatic; intervention indicated	<3.0 - 2.5; hospitalization indicated
Glucose – Hypoglycemia ** ⁽¹⁾ (mg/dL) (mmol/L)	<LLN - 55; <LLN - 3.0	<55 – 40; <3.0 – 2.2	<40 – 30; <2.2 – 1.7
Glucose – Hyperglycemia: ** ⁽¹⁾ Fasting (mg/dL) (mmol/L) Non-fasting (mg/dL) (mmol/L)	>ULN-160; >ULN-8.9 - -	>160-250; >8.9-13.9 - -	- - >250-500; >13.9-27.8; hospitalization indicated
Blood Urea Nitrogen (BUN) (mg/dL) ⁽²⁾	23 – 26	27 – 31	> 31
Creatinine increased** ⁽¹⁾	>1 – 1.5 x baseline; >ULN – 1.5 x ULN	>1.5 – 3.0 x baseline; >1.5 – 3.0 x ULN	>3.0 x baseline; >3.0 – 6.0 x ULN
Albumin – Hypoalbuminemia** ⁽¹⁾ (g/dL) (g/L)	<LLN - 3; <LLN - 30	<3 – 2; <30 - 20	<2; <20
Total Protein – Hypoproteinemia ⁽²⁾ (g/dL)	5.5 – 6.0	5.0 – 5.4	< 5.0
Alkaline phosphatase increased** ⁽¹⁾	>ULN – 2.5 x ULN	>2.5 – 5.0 x ULN	>5.0 – 20.0 x ULN
ALT / AST increased** ⁽¹⁾	>ULN – 3.0 x ULN	>3.0 – 5.0 x ULN	>5.0 – 20.0 x ULN
Gamma-glutamyl transferase (GGT) increased ⁽¹⁾	>ULN – 2.5 x ULN	>2.5 – 5.0 x ULN	>5.0 – 20.0 x ULN
Blood bilirubin increased ** ⁽¹⁾	>ULN – 1.5 x ULN	>1.5 – 3.0 x ULN	>3.0 – 10.0 ULN
Cholesterol high** ⁽¹⁾ (mg/dL)	>ULN - 300; >ULN - 7.75	>300-400; >7.75-10.34	>400-500; >10.34-12.92

Data and information contained in this document are considered to constitute trade secrets and confidential commercial information, and the legal protections provided to such trade secrets and confidential information are hereby claimed under the provisions of United States law. No part of this document may be publicly disclosed without the written consent of Philip Morris International.

(mmol/L)			
Triglycerides - Hypertriglyceridemia ⁽¹⁾			
(mg/dL)	150 – 300;	>300 – 500;	>500 – 1000;
(mmol/L)	1.71 – 3.42	>3.42 – 5.70	>5.70 – 11.40

Abbreviations: ALT = alanine aminotransferase; AST = aspartate aminotransferase; BUN = blood urea nitrogen; GGT = gamma-glutamyl transferase; LLN = lower limit of the normal range; ULN = upper limit of the normal range.

Data Sources:

(1) Common Terminology Criteria for Adverse Events (CTCAE) version 4.03. Toxicity Grading Scale for Healthy Adult and Adolescent Volunteers Enrolled in Preventive Vaccine Clinical Trials, U.S. Department of Health and Human Services, FDA, Center for Biologics Evaluation and Research - Guidance for Industry.

(2) Toxicity Grading Scale for Healthy Adult and Adolescent Volunteers Enrolled in Preventive Vaccine Clinical Trials, U.S. Department of Health and Human Services, FDA, Center for Biologics Evaluation and Research - Guidance for Industry.

* Those parameters that are not listed do not have grading categories in either the CTCAE or the FDA guidance documents and will therefore be reviewed by the Investigator and only reported as an AE if considered to be clinically relevant.

** Where parameters in this table are listed in both the CTCAE and the FDA guidance documents, and each document has different values within each grading category, the grading in CTCAE guidance document predominates.

ABNORMAL LABORATORY VALUES RATING: HEMATOLOGY PARAMETERS

Hematology*	Mild (Grade 1)	Moderate (Grade 2)	Severe (Grade 3)
Hemoglobin (Female) – (g/dL) ⁽¹⁾ change from baseline value – (g/dL) ⁽¹⁾	11.0 – 12.0 Any decrease – 1.5	9.5 – 10.9 1.6 – 2.0	8.0 – 9.4 2.1 – 5.0
Hemoglobin (Male) – (g/dL) ⁽¹⁾ change from baseline value – (g/dL) ⁽¹⁾	12.5 – 13.5 Any decrease – 1.5	10.5 – 12.4 1.6 – 2.0	8.5 – 10.4 2.1 – 5.0
Hemoglobin increase – (g/dL) ⁽²⁾	Increase in >0 – 2 above ULN or above baseline if baseline is above ULN	Increase in >2 – 4 above ULN or above baseline if baseline is above ULN	Increase in >4 above ULN or above baseline if baseline is above ULN
WBC Increase – (cell/mm ³) ⁽¹⁾	10,800 – 15,000	15,001 – 20,000	20,001 – 25,000
WBC Decrease - (cell/mm ³) ^{(2)**}	<LLN – 3000; <LLN – 3.0 x 10 ⁻⁹ /l	<3000 - 2000; <3.0 – 2.0 x 10 ⁻⁹ /l	<2000 - 1000; <2.0 – 1.0 x 10 ⁻⁹ /l
Lymphocytes Increase - (cell/mm ³) ⁽²⁾	-	>4,000 – 20,000	>20,000
Lymphocytes Decrease - (cell/mm ³) ^{(2)**}	<LLN – 800; <LLN – 0.8 x 10 ⁻⁹ /l	<800 - 500; <0.8 – 0.5 x 10 ⁻⁹ /l	<500 - 200; <0.5 – 0.2 x 10 ⁻⁹ /l
Neutrophils Decrease - (cell/mm ³) ^{(2)**}	<LLN – 1500; <LLN – 1.5 x 10 ⁻⁹ /l	<1500 - 1000; <1.5 – 1.0 x 10 ⁻⁹ /l	<1000 - 500; <1.0 – 0.5 x 10 ⁻⁹ /l
Eosinophils - (cell/mm ³) ⁽¹⁾	650 – 1500	1501 - 5000	>5000
Platelets Decrease - (cell/mm ³) ^{(2)**}	<LLN – 75,000; <LLN – 75.0 x 10 ⁻⁹ /l	<75,000 – 50,000; <75.0 – 50.0 x 10 ⁻⁹ /l	<50,000 – 25,000; <50.0 – 25.0 x 10 ⁻⁹ /l

Abbreviations: LLN = lower limit of the normal range; ULN = upper limit of the normal range; WBC = white blood cell.

Data Source:

(1) Toxicity Grading Scale for Healthy Adult and Adolescent Volunteers Enrolled in Preventive Vaccine Clinical Trials, U.S. Department of Health and Human Services, FDA, Center for Biologics Evaluation and Research - Guidance for Industry.

(2) Common Terminology Criteria for Adverse Events (CTCAE) version 4.03.

* Those parameters that are not listed do not have grading categories in either the CTCAE or the FDA guidance documents and will therefore be reviewed by the Investigator and only reported as an AE if considered to be clinically relevant.

** Where parameters in this table are listed in both the CTCAE and the FDA guidance documents, and each document has different values within each grading category, the grading in CTCAE guidance document predominates.

ABNORMAL LABORATORY VALUES RATING: URINALYSIS PARAMETERS

Urine*	Mild (Grade 1)	Moderate (Grade 2)	Severe (Grade 3)
Protein** ⁽¹⁾	1+ proteinuria; urinary protein <1.0 g/24 hours	2+ proteinuria; urinary protein 1.0-3.4 g/24 hours	Urinary protein ≥3.5 g/24 hours
Glucose ⁽²⁾	Trace	1+	2+
Blood – Hematuria ** ⁽¹⁾	Asymptomatic; clinical or diagnostic observations only; intervention not indicated	Symptomatic; urinary catheter or bladder irrigation indicated; limiting instrumental ADL	Gross hematuria; transfusion, IV medications or hospitalization indicated; elective endoscopic, radiologic or operative intervention indicated; limiting self-care ADL

Abbreviations: ADL = activities of daily living; IV = intravenous.

Data Source:

(1) Common Terminology Criteria for Adverse Events (CTCAE) version 4.03.

(2) Toxicity Grading Scale for Healthy Adult and Adolescent Volunteers Enrolled in Preventive Vaccine Clinical Trials, U.S. Department of Health and Human Services, FDA, Center for Biologics Evaluation and Research - Guidance for Industry.

* Those parameters that are not listed do not have grading categories in either the CTCAE or the FDA guidance documents and will therefore be reviewed by the Investigator and only reported as an AE if considered to be clinically relevant.

** Where parameters in this table are listed in both the CTCAE and the FDA guidance documents, and each document has different values within each grading category, the grading in CTCAE guidance document predominates.

Appendix 7 Procedure for Nasal Epithelial Collection

Materials to prepare ahead before sample collection:

- 2 Cyto-Pak soft brushes (Item #CP-5B, Medical Packaging Corporation)
- 2 of 2-mL round bottom microfuge tube with cap, sterile (Fisher Scientific Catalog # 02-681-375), containing: 1mL RNAProtect Cell Reagent (Qiagen Catalog #76526). These tubes are labeled "a" and "b" for first and second sampling, respectively
- Nasal speculum (Bionix # 9877, Bionix Medical Technologies, Toledo, OH)
- 1% Lidocaine Solution may be administered at participant request using a syringe with removable needle, which would be removed prior to use.
- RNaseZap (Ambion Catalog # AM9780; or AM9782) to decontaminate equipment and working area before handling the biological material.
- Tube rack
- Tube labels
- Wire cutter
- 70% isopropyl alcohol wipes (Fisher Scientific Catalog # 19-015-744)
- Liquid nitrogen or a quick access to -80°C storage

Protocol for the preparation of the nasal collection:

1. Ask subject to blow his/her nose
2. Place the two of 2-mL round bottom microfuge tubes filled with 1 mL RNAProtect Cell Reagent in the tube.
3. Treat the wire cutter with few sprays of RNaseZap, wipe the cutter with paper towels, then wipe the cutter with 2 isopropyl alcohol wipes
4. If the subject wishes to have the nostril numbed for the procedure, use a 1% Lidocaine Solution.
 - A. Draw 1 mL of Lidocaine into a syringe with a removable needle. Remove the needle once completed.
 - B. Have the participant hold a paper towel under his/her nose.
 - C. Have the participant verbally and rapidly repeat the letter "K" over and over again. Explain that this helps prevent the Lidocaine from getting into the throat, which can feel/taste unpleasant.

Data and information contained in this document are considered to constitute trade secrets and confidential commercial information, and the legal protections provided to such trade secrets and confidential information are hereby claimed under the provisions of United States law. No part of this document may be publicly disclosed without the written consent of Philip Morris International.

D. While the participant is saying the letter "K", quickly administer the Lidocaine into the nostril against the outside of the nose, which is opposite the septum.

Protocol of the nasal collection:

1. Use the nasal speculum to widen the left nostril then locate the inferior turbinate (a pen light may help to visualize the area
 - 1.1. While the speculum still widening the nostril, insert the Cyto-Pak soft brush into the nostril just past the inferior turbinate and press against the outside of the nostril (opposite from the septum) while being rotated. This step should take approximately 3 seconds
 - 1.2. Remove the Cyto-Pak soft brush from the nostril and immediately place the brush head in the 2-mL round bottom microfuge tube filled with 1 mL RNAprotect Cell Reagent (tube "a" for the first collection)
 - 1.3. Cut off the shaft of the brush with the cleaned wire cutter
 - 1.4. Repeat steps 1.1.-1.3. with the second Cyto-Pak soft brush (in the same nostril) for the second collection that will be collected in tube "b"
2. Vortex sample to ensure that all collected cells come into contact with the RNAprotect Cell Reagent
3. Store samples at -80°C

Note: All samples should not undergo any freeze-thaw cycle prior to shipping.

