6.7 Concomitant Medication

No medication should be taken during the study from the screening to the EOS (time of discharge from Day 90 Visit (Day 91) plus 28 days safety follow-up period) without prior informing the Investigator. However, the Investigator is responsible for the medical care of the subjects during their participation in this study. Any decisions regarding the prescribing of medication will be made in the best interests of the subject.

Data and information contained in this document are considered to constitute trade secrets and confidential commercial information, and the legal protections provided to such trade secrets and confidential information are hereby claimed under the provisions of United States law. No part of this document may be publicly disclosed without the written consent of Philip Morris International.

In the SA arm, subjects may be provided with NRT if considered necessary by the Investigator or requested by the subject. The use of medication supportive for smoking abstinence other than NRT will not be allowed.

Concomitant use of NSAIDs and acetylsalicylic acid (including over-the-counter products) is not allowed, as all of them could interfere with risk markers such as 11-DTX-B2. Acetaminophen will be allowed at a daily total dose of up to 3000 mg. Any medication (except medication containing estrogen) with an impact on the CYP1A2 and CYP2A6 metabolism (as prescription and over-the-counter products) as shown in Table 3 must be avoided.

If the use of a concomitant medication cannot be avoided for the subject's safety, it must be fully documented in the Source Document and transcribed into the eCRF (for details, see Section 7.4.7).

The drugs and substances shown in Table 3 are a selection of drugs considered to have an impact on CYP1A2 and/or CYP2A6 activity (Chang et al., 1999, Ingelman-Sundberg et al., 1999, Lacy et al., 2007). Prior to database close, concomitant medication will be assessed according to their potential impact on CYP1A2 and CYP2A6 activity and potential impact on the study results.

Concomitant medication will first be assessed at the Screening Visit. To be eligible for the study, any medication with impact on CYP1A2 and CYP2A6 metabolism must be discontinued at least 2 weeks prior to Admission to the clinic or for at least 5 half-lives (whichever is longer). They must not be used during the entire study until the Day 91 (completion of the study).

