Medication containing estrogens (e.g. for contraception and for hormone replacement therapy), even though known to be CYP1A2 inhibitors, will be allowed in this study but must be documented on the eCRF.

Table 3. Examples of Medications with Effects on CYP1A2 and CYP2A6 Activity

Drug name	Substance Class
Rifampicin and fluoroquinolones including ciprofloxacin and ofloxacin,	Antibiotics
Fluvoxamine, fluoxetine, paroxetine, bupropion, duloxetine, amitriptyline, imipramine, sertraline, mirtazapine, citalopram, thioridazine	Antidepressant
Haloperidol, perphenazine, chlorpromazine, propoxyphene fluphenazine, clozapine, olanzapine	Neuroleptic
Phenobarbital, primidone, carbamazepine	Antiepileptic
Cholorquine, quinidine	Antirheumatic
Clotrimazole, terbinafine, fluconazole, ketoconazole, miconazole	Antimycotic
Erythromycin, ciprofloxacin, clarithromycin, norfloxacin	Antibiotic
Cimetidine, chlorpheniramine, diphenhydramine, ranitidine	H ₂ -receptor antagonist
Amiodarone, verapamil, mibepradil, mexiletin, propafenone, propranolol, lidocaine	Antiarrhythmic
Losartan, amlodipine, nifedipine,	Antihypertensive
Drospirenone, estrogens	Hormonal contraception, hormonal replacement therapy (estrogens)
Fluvastatin	Cholesterol-lowering agent
Theophylline	Antispasmodic pulmonological agent/Bronchodilator agent
Omeprazole, lansoprazole	Proton pump inhibitor
Interferon	Antiviral/Immunomodulating agent
Methoxsalen	Anti-psoriatic
Modafinil, diclofenac, rofecoxib	Analgesic
Insulin	Anti-diabetic

Data and information contained in this document are considered to constitute trade secrets and confidential commercial information, and the legal protections provided to such trade secrets and confidential information are hereby claimed under the provisions of United States law. No part of this document may be publicly disclosed without the written consent of Philip Morris International.

Drug name	Substance Class
Sildenafil	Erectile dysfunction
Quinine	Leg cramps
St. John's Wort	Over-the-counter (herbal remedy) antidepressant
Psoralen	Anti-psoriatic (substance class Furocoumarins)
Pilocarpine	Cholinergic agonists (e.g., used for Glaucoma Therapy)

Data sources: Chang et al., 1999, Ingelman-Sundberg et al., 1999, Lacy et al., 2007. The list is not exhaustive.

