7.4.7 Medical History, Concomitant Disease, Previous and Ongoing Medications

Relevant medical history will be documented at the Screening Visit. Any concomitant disease will be documented at the Screening Visit. Medical history is defined as any condition that started prior to and ended prior to Screening. A concomitant disease is defined as any condition that started prior to the Screening Visit and is still ongoing at the Screening Visit.

Prior medication taken 4 weeks prior to Screening Visit and any concomitant medication needs to be documented. Any medication which was started prior to the Screening Visit and is still being taken by the subject will be considered a concomitant medication. Medication initiated after Screening is also referred to as concomitant medication. This applies to both prescription and over-the-counter products.

Records of any medication taken must include the drug name (preferably both generic and trade name), route of administration (e.g., oral, intravenous), total daily dose/unit (e.g. expressed in mg, mL, or IU), indication, the start and (if applicable), the stop date (day, month and year). Any therapy changes (including changes of regimen) during the study are to be documented. Any concomitant medication that is still being taken by the subject at the EOS will be recorded on the eCRF.

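### Appendix 7 lets staff give intranasal lidocaine on request, although section 6.7 and Table 3 bar it until Day 91, and the schedule allows it ahead of CYP1A2 and CYP2A6 samples

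*Protocol*

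**What the plan says.** **The nasal procedure.** Protocol Appendix 7, step 4, reads "If the subject wishes to have the nostril numbed for the procedure, use a 1% Lidocaine Solution". The dose follows: "Draw 1 mL of Lidocaine into a syringe with a removable needle". Section 7.7.3.2 foresees this use and asks only for a check on lidocaine allergy. Collection is optional, under a separate bio-banking consent, on Days 0, 6 and 90.

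**The medication rule.** Protocol section 6.7 covers "Any medication (except medication containing estrogen) with an impact on the CYP1A2 and CYP2A6 metabolism" and requires the Table 3 drugs to be avoided. On duration it says "They must not be used during the entire study until the Day 91". The antiarrhythmic row of Table 3 reads "Amiodarone, verapamil, mibepradil, mexiletin, propafenone, propranolol, lidocaine". Oestrogen-containing medication is the one named exemption. A separate clause allows medication that the subject's safety makes unavoidable, provided that it is documented.

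**The schedule.** On Day 0 (Table 10) the caffeine tablet is taken at 10:00-11:30 AM, the CYP1A2 draw is at 04:00-05:30 PM, and the nasal collection is at any point in the afternoon up to 09:00 PM. On Day 90 (Table 18) the tablet comes with breakfast before 11:00 AM, the CYP1A2 draw follows 6 hours later, and the nasal window is the same. CYP2A6 is drawn on Day 91 before product use. On Day 6 (Table 16) CYP2A6 is drawn before product use, and the nasal row has no clock time. SAP Table 23 gives the same window for Days 0 and 90, and any time before discharge for Day 6, with no order relative to the CYP samples.

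**The analysis.** SAP 12.6.2.4 (CYP1A2) and 12.6.3.4 (CYP2A6) analyse the PP Set and the FAS. Each then repeats the analysis without assessments made within 5 half-lives of a medication affecting that enzyme. SAP Table 22 classes use of such a drug as a minor deviation.

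**The concern.** Section 6.7 tells staff that lidocaine may not be used, and Appendix 7 tells them to give it when asked. Numbing for comfort is neither an oestrogen nor unavoidable for safety, so neither exception applies. Following the study's own procedure therefore produces what the SAP counts as a deviation.

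The sequence matters too. The step can expose a CYP1A2 sample (secondary endpoint) or a CYP2A6 sample (exploratory endpoint) to a drug that the protocol itself lists as interfering. Afterwards the SAP can only drop that sample in a repeat analysis. The main analysis keeps it.

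**Working it through.** The plan states no figure to reproduce here. The check sets the texts side by side and adds clock and dose arithmetic.

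1. **Dose.** A 1% solution is 10 mg/mL, so 1 mL × 10 mg/mL = 10 mg per collection. Three collection days allow up to 3 × 10 = 30 mg in total.

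2. **Day 0 clock.** I assume that the afternoon starts at noon, so the nasal window runs 9 h, from 12:00 to 21:00. The scheduled draw at 16:00-17:30 leaves 4.0 to 5.5 h of that window before it (4/9 = 44% to 5.5/9 = 61%). Using the tablet time plus 6 h ± 15 min instead, the draw falls at 15:45-17:45, which is 3.75 to 5.75 h in. These are hours on the clock, not a probability of exposure.

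3. **Day 90 clock.** The latest tablet at 11:00 gives a latest draw at 11:00 + 6 h 15 min = 17:15, so up to 5.25 h of the window precede it. No earliest tablet time is given. If 09:00 is assumed, the earliest draw is 14:45, and 2.75 h precede it.

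4. **Day 91.** A nasal collection on Day 90 ends by 21:00, and CYP2A6 is drawn the next day. Lidocaine given on Day 90 therefore always comes first. Placing the collection after the CYP1A2 draw on Day 90 does not change this and brings the lidocaine closer to the CYP2A6 sample.

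5. **Does row order settle the sequence?** The CYP1A2 rows stand above the nasal rows, but no text makes row order binding. Table 18 lists dinner, due before 09:00 PM, below questionnaires scheduled for 08:00-11:00 PM. Where order matters the protocol says so, as with COHb before gas transfer.

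6. **Where an exposed sample goes.** Under SAP 10.2 only major deviations that affect evaluability remove a subject from the PP Set, and Table 22 makes this one minor. The value therefore stays in the main PP and FAS analyses and leaves only the repeats. A Day 0 CYP1A2 value dropped from a repeat also removes that subject from the Day 5 and Day 90 repeat models, because log baseline is a model term and CYP1A2 has no earlier measurement to use instead.

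7. **Precision lost in a repeat analysis, per excluded Day 0 value.** The ratio of CI widths, ignoring covariates and degrees of freedom, is the square root of the ratio of (1/n₁ + 1/n₂) after and before the loss:
   - Day 5, 80:40, one mCC or SA subject lost: √[(1/80 + 1/39)/(1/80 + 1/40)] = 1.0085, about 0.9% wider.
   - Day 5, 80:40, one THS subject lost: √[(1/79 + 1/40)/(1/80 + 1/40)] = 1.0021, about 0.2% wider.
   - Day 90 PP versus mCC at the planned 40:40, one subject lost from either arm: √[(1/40 + 1/39)/(1/40 + 1/40)] = 1.0064, about 0.6% wider.

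8. **Traceability.** Section 7.4.7 asks for medication start and stop dates, not clock times, so the medication record cannot order lidocaine and a draw on the same day. The nasal collection time is needed as well.

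**The case against.** The strongest reply is that nothing in the documents shows harm. Table 3 is headed as examples, files lidocaine under antiarrhythmics, and is described as "a selection of drugs considered to have an impact on CYP1A2 and/or CYP2A6 activity". It therefore does not say which enzyme lidocaine affects, and gives no effect for 10 mg in the nostril. This stands: no bias in either metabolic ratio can be claimed or quantified.

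A second reply is that safeguards exist. Section 6.7 says "Prior to database close, concomitant medication will be assessed according to their potential impact on CYP1A2 and CYP2A6 activity", and the SAP prespecifies the repeat analyses. CYP1A2 sampling times must be recorded, and SAP Table 22 has a time-deviation category that covers nasal collection, so the order is probably recoverable. This stands in part. These steps act after exposure, depend on the lidocaine having been recorded and judged relevant, and leave the main analyses unchanged.

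A third reply is that staff would simply follow the specific procedure, so that only a cross-reference is missing. In practice they probably would, but the procedure is then a breach of section 6.7 as written.

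Day 6 carries least weight. Neighbouring rows and the SAP place the collection before discharge, the blank time may be a table artefact, no CYP1A2 sample is drawn that day, and the CYP2A6 draw comes before product use. An order there is a precaution.

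**Conclusion.** The inconsistency between Appendix 7 and section 6.7 is real. The schedule permits lidocaine before the CYP1A2 draw on Days 0 and 90, and guarantees that any Day 90 dose precedes the Day 91 CYP2A6 draw. Whether it matters rests on the protocol's own listing of lidocaine as interfering, which the documents neither quantify nor tie to one enzyme. Neither the number consenting to nasal collection nor the number asking for numbing is given. The number affected is probably small, and each Day 0 value excluded from a repeat costs 0.2% to 0.9% in CI width. This is a cheap improvement, not a threat to the trial's conclusions.

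A reader might infer three things that the documents do not support:
- **That the CYP results are biased.** No effect of this dose and route is given.
- **That subjects would leave the PP Set or the trial, or that a primary endpoint is touched.** The deviation is minor, and section 5.1.3 makes discontinuation for unauthorised medication discretionary. The primary endpoints are exposure biomarkers, not CYP activity.
- **That the main CYP analyses are safe because the repeats exist.** If lidocaine interferes, the main analyses are the ones that keep the exposed values.

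**What to change.** **Simplest change.** Delete the lidocaine option from Appendix 7 (materials list and step 4) and from section 7.7.3.2. The cost is slight discomfort in an optional procedure of two brushings of about 3 seconds each.

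**If lidocaine is kept:**
- Add a stated exception for it to section 6.7.
- Day 0 (Table 10): require the nasal collection to follow that day's CYP1A2 draw. The latest draw is 17:45, which leaves 21:00 − 17:45 = 3.25 h of the existing window.
- Day 6 (Table 16): require it to follow the CYP2A6 draw.
- Day 90 Visit (Table 18 and SAP Table 23): either offer no lidocaine, or move the nasal collection to Day 91 after the CYP2A6 draw. Ordering it after the Day 90 CYP1A2 draw alone is not enough. The move also means changing the Day 90 date in sections 6.6.2.2 and 7.7.3.2 and in the Appendix 1 schedule.

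Either route costs a few sentences and adds no procedure or sample.
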